11. PLANNED STATISTICAL METHODS

11.1. General Considerations

Details regarding the statistical analyses will be provided in the Statistical Analysis Plan (SAP), which will be finalized prior to database lock and unblinding.

Continuous variables will be summarized using the number of observations, mean, standard deviation (SD), median, minimum, and maximum. Categorical variables will be summarized using frequency counts and percentages.

For Double Blinded Treatment Period, hypotheses tests will be performed for efficacy endpoints for the comparison of etrasimod dose versus the placebo group. However, these hypotheses tests will not be controlled for type-I error rate. Un-adjusted p-values will be reported.

For the Extension Treatment Period, no hypothesis tests between treatment groups will be performed; only descriptive statistics will be provided.

The SAP will describe an overall plan to address the alignment between the target of efficacy estimation (ie, trial objective, or estimand of interest), the analysis set, the method of estimation, and primary method to handle intercurrent events; along with a plan of sensitivity analysis to evaluate the robustness of findings that can sustain limitations in missing data and intercurrent events of non-adherence to protocol.

Efficacy data will be analyzed by randomized treatment, while safety data will be analyzed by actual treatment.

CCI [REDACTED]

[REDACTED]

11.3. Analysis Sets

For purposes of analysis, the following analysis sets are defined for each treatment period as shown in [Table 6](#).

Table 6: Analysis Sets

Analysis Set	Description
Full Analysis Set (FAS); (Double-Blind Treatment Period)	The FAS will include all randomized subjects in the Double-Blind Treatment Period, who receive at least 1 dose of study treatment. Subjects will be summarized by treatment to which they were randomized, regardless of treatment actually received.
Modified Full Analysis Set (mFAS); (Double-Blind Treatment Period)	The mFAS will include all randomized subjects who receive at least one dose of study medication and have a baseline measurement and have at least 1 post-randomization measurement. The mFAS is endpoint specific, therefore subjects included in the analysis set for one endpoint may differ from another endpoint, based on the baseline and post-baseline data.
Per Protocol Set; (Double-Blind Treatment Period)	The Per Protocol will include all subjects from the FAS without major protocol violations that might affect the evaluation of the effect of study treatment on the primary endpoint. The Per Protocol will be used in sensitivity analyses of the primary and secondary endpoints to evaluate the influence of major protocol violators and protocol deviators on the main efficacy results. Subjects may be excluded from this population if they violate the eligibility criteria or significantly deviate from the study plan. Specific reasons for warranting exclusion from this population will be documented prior to database lock and may include, but are not limited to, study treatment noncompliance, receiving incorrect study treatment, and missing more than a defined number of visits while still on study. The statistical analysis plan, which will be finalized prior to database lock, will be the final documentation for the Per Protocol Set definition.
Pharmacokinetic Set; (Double-Blind Treatment Period)	The Pharmacokinetic Set will include all subjects in the FAS with at least 1 postdose PK measurement.
Safety Set; (Double Blind Treatment Period and Extension Treatment Period)	The Safety Set will include all randomized subjects who received at least one dose of study treatment during the specified treatment period.
Efficacy Evaluable Set; (Extension Treatment Period)	The Efficacy Evaluable Set will include subjects who receive at least one dose of etrasimod and have at least one efficacy measurement in the Extension Treatment Period (endpoint specific)

Baseline for the Extension Treatment Period is defined as the last measurement prior to the first etrasimod dose started at Week 24.

11.4. Missing Data

11.4.1. Primary Methods of Handling Missing Data and Rescue Medication/Rescue Procedure Usage

In order to analyze efficacy endpoints at Week 16 and Week 24 in the Full Analysis Set (FAS), handling missing data and rescue medication uses are specified as following. For the endpoint of the percent change from Baseline in esophageal PEC at Week 16 and Week 24, PEC after rescue medication/rescue procedure use will be set to missing. All missing PEC at scheduled visits up to Week 24 will be imputed using a multiple imputation (MI) procedure with a fully conditional specification (FCS) method and predictive mean matching for PEC [64-66]. The use of rescue medication/rescue procedure, reasons for early discontinuation (eg, AE), and duration of study treatment prior to early discontinuation will be captured to address and characterize the nature of

missing data in the MI procedure with an FCS method. Detailed MI model descriptions and analysis procedures will be specified in the SAP.

For analysis of dichotomous endpoints (eg, proportion of subjects with esophageal PEC of < 15 and ≤ 6 eos/hpf at Week 16 and Week 24), all subjects in the FAS will be included in the analyses. Subjects in any of the following cases will be considered as a “non-responder” or “failure”:

- Use of rescue medications/rescue procedures during the Double-Blind Treatment Period;
- Prematurely discontinue from study due to any reason prior to Week 16 and Week 24; or
- With missing data at Week 16 and Week 24 for any reason

11.4.2. Sensitivity Analyses

In addition to the primary method for handling missing data and rescue medication/rescue procedure use in the FAS described in Section 11.4.1, the following sensitivity analyses will be performed for primary, secondary, and selected CCI using alternative methods to handle missing data and/or in alternative analysis populations:

- MI usually assumes that the data are missing at random (MAR) but MAR cannot be verified using the observed data. Therefore, the sensitivity of inferences to departures from the MAR assumption will be examined. For the MI analysis of the primary endpoint of percent change from Baseline in esophageal PEC at Week 16 and Week 24, data MAR within each treatment group will be investigated using tipping point analyses method and results will be described using Rubin’s rule [1]
- Percent change in esophageal PEC from Baseline to Week 16 and Week 24 will be analyzed in the modified Full Analysis Set (mFAS), data will be set to missing after rescue medication/rescue procedure uses
- Proportion of subjects with esophageal PEC of < 15 and ≤ 6 eos/hpf at Week 16 and Week 24 will be analyzed in the FAS using PEC imputed by the MI method discussed in Section 11.4.1
- Proportion of subjects with esophageal PEC of < 15 and ≤ 6 eos/hpf at Week 16 and Week 24 will be analyzed in the mFAS using PEC imputed by the MI method discussed in Section 11.4.1
- Observed data analyses in mFAS, regardless of rescue medication/rescue procedure use and without missing data imputation:
 - For longitudinal continuous variables, a linear mixed effects model will be performed and results will be reported by visit.
 - For longitudinal dichotomous measures, logistic regression analysis may be performed by visit
- Completers analyses (also known as complete case) of primary and secondary endpoints for subjects who complete 16 and 24 weeks of study treatment

- Per Protocol Set analyses in subjects who meet the criteria of Per Protocol definition approved prior to database lock

Detailed sensitivity analysis methods will be described in the SAP.

11.5. Efficacy Analyses

For the Double-Blind Treatment Period, the primary and secondary endpoints will be analyzed using the FAS. Other important statistical considerations, such as handling rescue medication/rescue procedure uses during study treatment, missing data imputation strategies, sensitivity analyses, and subgroup analyses will be described in the SAP.

The endpoints of percentage change in esophageal PEC from Baseline to Week 16 and Week 24 will be analyzed using analysis of covariance (ANCOVA) model based on rank scores due to the skewed distribution of the data and possible outliers. The ANCOVA model will include treatment group and randomization stratification factors as factors and Baseline eosinophil PEC as a covariate. PEC after rescue medication/rescue procedure uses will be set to missing; all missing data will be imputed in the FAS using MI procedure as appropriate. Multiple results of ANCOVA (least square [LS] mean rank scores and LS mean rank score difference from placebo) for each MI dataset will be analyzed and reported along with final p-value using Rubin's method [1]. In addition, a descriptive summary of percentage change in esophageal PEC from baseline as well as the difference between treatment groups will be presented by treatment group. When applying the same ANCOVA model to key secondary continuous variables, norank transformation will be used.

For the efficacy endpoints of the percentage change in esophageal PEC from Baseline at Week 16 and Week 24, in the FAS, subjects who have experienced intercurrent events, such as rescue medication/rescue procedure use, early discontinuation of study treatment, etc., will be included in the analysis and their missing data at Week 16 and Week 24 will be imputed using a MI model. The MI model will take into consideration the reason and nature of intercurrent event leading to missing data. A detailed plan for constructing and analyzing the primary estimand will be described in the SAP.

Proportion-based secondary endpoints (eg, histologic responders or symptomatic responders) at Week 16 will be analyzed in the FAS; subjects who use rescue medication or have a rescue procedure, or with missing data for any reason will be considered a "non-responder" or "failure." The analyses will be performed using the Cochran-Mantel-Haenszel (CMH) method adjusted for randomization stratification factors. The number and percentage of subjects achieving the goal and the difference in proportion between treatment groups achieving the goal, along with p-value and the 95% CIs will be reported.

Longitudinal continuous endpoints (Section 11.5.1.2) will also be analyzed up to Week 24 using a linear mixed effects model. The model will include treatment group, visit, interaction of treatment-by-visit, and randomization stratification factors as factors, and Baseline measure as covariates. An unstructured covariance matrix will be specified for the within-subject measurements. LS means and LS mean differences between treatment group with unadjusted p-values and corresponding 95% CIs will be reported at each scheduled visit. This method will also be applied to other score based or continuous measures.

CCI

Endpoints measured during the Extension Treatment Period after Week 24 up to Week 52 will be summarized using descriptive statistics without inferential comparison. Dichotomous remission or response outcomes derived from specific scores will be assessed. Continuous variables will be summarized by visit using the number of observations, mean, SD, median, minimum, and maximum; and categorical variables will be summarized by visit using frequency counts and percentages, with following considerations:

- Four treatment sequence (as listed below) in the Extension Treatment Period will be analyzed, if applicable
 - etrasimod 1 mg-1 mg
 - etrasimod 2 mg-2 mg
 - placebo - etrasimod 1 mg
 - placebo - etrasimod 2 mg
- Change from baseline in continuous variables will be analyzed on change from Baseline in the Double-Blind Treatment Period and change from Baseline in the Extension Treatment Period

CCI

In addition to between group analyses on the primary and secondary endpoints, dose-response relationship will be investigated using exposure-response modeling and the details will be described in the PK/PD analysis document. The PK/PD modeling will be written as a standalone document.

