Study Design: 
This Phase 2, randomized, double-blind, multi-center study will evaluate the efficacy, safety, and pharmacokinetics (PK) of etrasimod compared with placebo in adults with active EoE. The study will consist of a Screening Period of up to 35 days, 24 weeks of double-blind treatment (Double-Blind Treatment Period), 28 weeks of active extended treatment (Extension Treatment Period), and 4 weeks of follow-up (Safety Follow-Up Period) for a total study duration of up to 61 weeks.
 
Eligible subjects will be randomized in a double-blind fashion (3:3:2 ratio) to etrasimod 1 mg, etrasimod 2 mg, or matching placebo once daily. Randomization will be stratified by baseline history of esophageal dilation (yes/no) and concurrent proton pump inhibitor (PPI) therapy (yes/no).
 
All subjects who complete the Double-Blind Treatment Period and meet eligibility criteria for the Extension Treatment Period may enter the Extension Treatment Period. Subjects who were in the etrasimod 1 mg or etrasimod 2 mg groups in the Double-Blind Treatment Period will continue the same etrasimod dose in the Extension Treatment Period. Subjects who were in the placebo group during the Double-Blind Treatment Period will be re-randomized (1:1 ratio) to etrasimod 1 mg or etrasimod 2 mg at entry into the Extension Treatment Period.
 
Subjects will have follow-up visits at 2 and 4 weeks after the last dose of study treatment after Week 52 or the Early Termination (ET) Visit.

Number of Subjects (planned):

Approximately 96 subjects are planned to be enrolled.

Eligibility Criteria for the Double-Blind Treatment Period:

Key Inclusion Criteria (Full Inclusion Criteria Are Provided in the Protocol)

- Men or women between 18 and 65 years of age at the time of informed consent (IC)
- Have an EoE diagnosis prior to screening and histologically active disease with an esophageal peak eosinophil count (PEC) of ≥ 15 eosinophils (eos)/high power field (hpf) (~ 60 eos/mm²) from any level (proximal, mid, or distal) of the esophagus at the Screening esophagogastroduodenoscopy (EGD)
- Have dysphagia, defined as solid food going down slowly or getting stuck in the throat with an average frequency of ≥ 2 episodes per week over 2 weeks (as documented using the Dysphagia Symptom Questionnaire (DSQ) during the Screening period)

Key Exclusion Criteria (Full Exclusion Criteria Are Provided in the Protocol)

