2. OBJECTIVES

Primary:

- To evaluate the effects of etrasimod on esophageal eosinophilia in adult subjects with active EoE
- To evaluate the dose-response relationship of 2 doses of etrasimod versus placebo in adult subjects with active EoE
- To select an etrasimod dose based on efficacy and safety for continued development

Secondary:

- To evaluate the effect of etrasimod on dysphagia symptoms in adult subjects with active EoE

CCI [REDACTED]

- [REDACTED]
- [REDACTED]
- [REDACTED]
- [REDACTED]

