11.7. Testing Strategy

For Double Blinded Treatment Period, hypotheses tests will be performed for efficacy endpoints for the comparison of etrasimod dose versus the placebo group. However, these hypotheses tests will not be controlled for type-I error rate. Un-adjusted p-values will be reported. The associated 95% confidence intervals will be reported.

For the Extension Treatment Period, no hypothesis tests between treatment groups will be performed; only descriptive statistics will be provided.

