17.1.4. PRIMARY ANALYSIS OF PRIMARY EFFICACY VARIABLE(S)

The following hypotheses (H01 and H02) for the primary endpoint will be tested:

H₀₁: The percentage change from Baseline in esophageal PEC at Week 16 is the same between etrasimod 2mg and placebo.

H₁₁: The percentage change from Baseline in esophageal PEC at Week 16 is different between etrasimod 2mg and placebo.

H₀₂: The percentage change from Baseline in esophageal PEC at Week 16 is the same between etrasimod 1mg and placebo.

H₁₂: The percentage change from Baseline in esophageal PEC at Week 16 is different between etrasimod 1mg and placebo.

All hypotheses will be tested at the 2 sided α level, 0.05.

The primary efficacy analysis will be performed for the FAS. Percent change from baseline in esophageal PEC will be summarized using the number of observations, mean, standard deviation (SD), median, minimum, and maximum. An analysis of covariance (ANCOVA) model based on rank scores due to the skewed distribution of the data and possible outliers will be used. The ANCOVA model will include treatment group and randomization stratification factors of Baseline history of esophageal dilation (Yes/No) and concurrent PPI therapy (Yes/No) as factors and Baseline eosinophil PEC as a covariate. Multiple results of the ANCOVA model will be expressed as least square (LS) means rank scores, LS mean rank scores difference from placebo, 95% confidence interval (CI) and p-value. For the treatment comparisons of etrasimod 1 mg vs. placebo and etrasimod 2 mg vs placebo, the treatment group factor in the ANCOVA model will include placebo, etrasimod 1 mg and etrasimod 2 mg. For the comparison of etrasimod any dose vs placebo, a separate ANCOVA model based on rank scores will be used, where treatment group factor will only include placebo and etrasimod any dose treatment. For the Extension Treatment Period, no pair-wise comparison will be performed; only descriptive statistics will be provided. In addition, descriptive summary of percentage change in esophageal PEC from baseline as well as difference between treatment groups will be presented by treatment group.

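### Dose-response and dose selection are primary objectives, but the visible plan names only contrasts with placebo and specifies no 2 mg minus 1 mg estimate

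*Protocol*

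**What the plan says.** Protocol section 2 lists three primary objectives, and SAP 2.1 repeats them. One is "To evaluate the dose-response relationship of 2 doses of etrasimod versus placebo in adult subjects with active EoE". Another is "To select an etrasimod dose based on efficacy and safety for continued development".

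The analyses named in the visible text are these:

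- **Primary endpoint (SAP 17.1.4).** The two hypotheses are 2 mg against placebo and 1 mg against placebo. "For the treatment comparisons of etrasimod 1 mg vs. placebo and etrasimod 2 mg vs placebo", one ANCOVA on rank scores carries all three arms. A separate two-group model compares any dose with placebo. "All hypotheses will be tested at the 2 sided α level, 0.05".
- **Estimands (SAP 2.4).** All five summary measures are differences from placebo for 2 mg, 1 mg and any dose.
- **Continuous secondary endpoints (SAP 17.2.3.1).** The treatment differences are spelled out as 1 mg, 2 mg and pooled, each against placebo.
- **Testing strategy (Protocol 11.7, SAP 8.4).** The tests compare etrasimod dose with placebo, and "these hypotheses tests will not be controlled for type-I error rate". Unadjusted p-values and 95% CIs are reported.
- **Dose-response (Protocol 11.5).** In addition to the between-group analyses, "dose-response relationship will be investigated using exposure-response modeling and the details will be described in the PK/PD analysis document". SAP section 19 adds exploratory exposure-response scatter plots.

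Protocol 6.5 mentions a dose selection analysis at Week 24, but no visible section says what it contains.

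**The concern.** A trial meant to choose between two doses should estimate how the two doses differ. Here the randomized 2 mg versus 1 mg difference is available in the planned three-arm model but is not listed as an output.

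Without it, a reader has two placebo contrasts to set side by side. They share a placebo arm, and one may fall below 0.05 while the other does not. That pattern is easily read as a dose effect, although it can arise when the doses are equally effective.

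Exposure-response modeling does not fill the gap. Subjects are randomized to dose, not to concentration, so within a dose the relation between trough level and response is observational. At stake is whether two primary objectives have a pre-specified analysis that rests on randomization.

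**Working it through.** **Inputs.** The protocol synopsis gives "Approximately 96 subjects are planned to be enrolled", "randomized in a double-blind fashion (3:3:2 ratio) to etrasimod 1 mg, etrasimod 2 mg, or matching placebo once daily". So 96 × 3/8 = 36 on each dose and 96 × 2/8 = 24 on placebo. Alpha is 0.05 two-sided (SAP 17.1.4). The sample-size rationale is redacted, so the total of 96 cannot be reproduced, and the effect sizes below are assumptions shown as a range. Calculations are in SD units with a normal approximation. They ignore covariate adjustment, ranking and multiple imputation.

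**Step 1: precision.** SE = √(1/n₁ + 1/n₂) and 95% half-width = 1.96 × SE.

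| Contrast | SE (SD units) | 95% half-width | Detectable with 80% power |
|---|---|---|---|
| Either dose vs placebo (36 vs 24) | √(1/36 + 1/24) = 0.264 | 0.52 | 0.74 |
| 2 mg vs 1 mg (36 vs 36) | √(2/36) = 0.236 | 0.46 | 0.66 |

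With an assumed 10% or 20% loss, the 2 mg versus 1 mg half-width becomes 0.49 or 0.52 SD.

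**Step 2: how often the two placebo contrasts disagree when the doses are equal.** The test statistics share the placebo arm, so their correlation is (1/24)/(1/24 + 1/36) = 0.6. For a common true effect δ:

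- Each dose is significant with probability p = Φ(δ/0.264 − 1.96).
- Both are significant with probability b, from the bivariate normal distribution with correlation 0.6.
- Exactly one is significant with probability 2(p − b).

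| δ (SD) | p | b | Exactly one significant |
|---|---|---|---|
| 0.6 | 0.624 | 0.485 | 28% |
| 0.7 | 0.757 | 0.643 | 23% |
| 0.8 | 0.859 | 0.780 | 16% |
| 0.9 | 0.927 | 0.880 | 9% |

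Simulation gives the same percentages. In the simulated trials where only 2 mg was significant, a direct 2 mg versus 1 mg test was non-significant in 83% to 87% of cases over this range.

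**Step 3: an example.** Suppose p = 0.01 for 2 mg and p = 0.10 for 1 mg, each against placebo. The z values are 2.576 and 1.645. The implied direct statistic is (2.576 − 1.645) × 0.2635/0.2357 = 1.04, which gives p of about 0.30. The two results look different, but the doses are not shown to differ.

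**Step 4: what the direct contrast can resolve.** Power = Φ(d/0.236 − 1.96) for a true between-dose difference d. At 0.3, 0.4, 0.5 and 0.6 SD this is 25%, 40%, 56% and 72%. For a responder endpoint with assumed rates of 30% and 50%, the half-width of the risk difference is 1.96 × √(0.3×0.7/36 + 0.5×0.5/36) = 0.22.

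**The case against.** The strongest case on the other side has five parts.

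1. **The dose-response objective is itself worded against placebo.** The dose-versus-placebo contrasts therefore partly address it, and Protocol 11.5 presents the modeling as an addition to them. This stands. It does not cover the dose-selection objective, which asks for a choice between the doses.
2. **Some wording is generic.** Protocol 11.5 and SAP 17.1.4 promise differences between treatment groups in the descriptive summaries, and Protocol 11.5 does the same for responder and mixed-model outputs, without limiting them to placebo. This stands in part. SAP 17.2.3.1 closes that reading for the continuous secondary endpoints by listing its three contrasts. For the primary rank ANCOVA, SAP 17.1.4 specifies differences from placebo. What remains open is a descriptive difference with no pairs named, and the responder outputs.
3. **Text is redacted.** Blacked-out passages lie in Protocol 11.5 and after the start of SAP 17.2.3.2, and the PK/PD document is not available. A dose comparison there cannot be ruled out. The point is therefore limited to the visible plan, but the contrasts in SAP 17.1.4 and 17.2.3.1 are listed in readable text.
4. **The contrast may be inconclusive.** Two active doses may well differ by less than either differs from placebo, and step 4 shows modest power. This is a reason to report an interval and not to rely on a test.
5. **The primary model works on ranks.** A 2 mg minus 1 mg difference in mean rank score is hard to interpret clinically. This stands, but the absolute PEC and DSQ analyses in SAP 17.2.3.1 are on their natural scales.

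**Conclusion.** The visible plan specifies no 2 mg minus 1 mg estimate, although dose-response and dose selection are primary objectives. Dose selection on efficacy would rest largely on indirect comparison of two placebo contrasts. Under an assumed equal effect of 0.6 to 0.9 SD and full arms of 36, 36 and 24, these would disagree on significance in about 28% down to 9% of trials. Discordant significance is therefore not evidence that the doses differ.

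A reader might infer three stronger things that the documents do not support:

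- **That the dose will be picked by comparing two p-values.** No selection rule is stated. Effect estimates with 95% CIs, descriptive group differences, exposure-response work and safety by dose are all planned. The percentages show how misleading such a comparison would be, not that it is intended.
- **That no comparison between the doses can appear at all.** The generic wording and the redactions leave room for one.
- **That pooling the doses conceals the question.** The pooled contrast is a separate, additional model and replaces nothing.

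This is worth fixing because the change is cheap and serves stated primary objectives. It does not invalidate the planned placebo comparisons.

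**What to change.** Before the double-blind period is unblinded, add to SAP 17.1.4 and 17.2.3 the 2 mg minus 1 mg difference with its 95% CI, labelled as estimation and not as a powered test.

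- **Continuous endpoints:** take it from the three-arm ANCOVA and the three-arm mixed model already planned. This is one further contrast per model.
- **Responder endpoints (PEC <15 and ≤6 eos/hpf):** run a stratified Mantel-Haenszel risk difference of 2 mg versus 1 mg, using the same strata and non-responder rules. This is a separate run, not a contrast from a fitted model.

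A linear contrast over 0, 1 and 2 mg on the LS means is not needed. Its coefficients are −1, 0 and +1, so it equals the 2 mg versus placebo contrast already planned.

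The cost is a few more unadjusted outputs, with no extra subjects or data. The downside is an interval of about ±0.46 SD that may not settle a small dose difference, and the text should say so.
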